### 5.7 Criteria for Taking a Participant Off Study

Participants will be removed from study when any of the following criteria apply:

- Lost to follow-up
- Completion of 3 years of follow up
- Withdrawal of consent for data submission
- Death

The reason for taking a participant off study, and the date the participant was removed, must be documented in the case report form (CRF).

## 6. DOSING DELAYS/DOSE MODIFICATIONS

### 6.1 Elotuzumab

No dose reductions for elotuzumab are allowed. If Elotuzumab is held on Day 1 of a new cycle, treatment with Lenalidomide/Dexamethasone will also be delayed. If Elotuzumab is held during any cycle on days 8, 15, or 22, the treating investigator will decide if Lenalidomide will be held using recommended guidance for retreatment below. Dexamethasone should always be given with Elotuzumab. The dose of dexamethasone may be modified per guidance below. Treatment may be delayed for a maximum of 21 days. If a patient must discontinue treatment with lenalidomide, they may continue to receive elotuzumab on study after discussion with the overall principal investigator.

If a patient must discontinue elotuzumab for unacceptable toxicity, they may continue to receive lenalidomide and dexamethasone on study after discussion and approval of the overall principal investigator.

### 6.2 Lenalidomide

Patients may hold treatment of lenalidomide for up to 21 if the toxicity is considered either possibly, probably or definitely related to the drug. Patients may hold lenalidomide for greater than 21 days only after discussion and subsequent approval of the overall principal investigator.

**Hematologic Toxicities:** For adverse hematologic events that are considered possibly, probably or definitely related to Lenalidomide, the following criteria for retreatment and dose modification should be followed. Treatment may be held for a maximum of 21 days. Refer to Table 4 for dose reduction levels for Lenalidomide.

CONFIDENTIAL

This document is confidential. Do not disclose or use except as authorized.

**Non Hematologic Toxicity:** For adverse non hematologic events that are considered to be possibly, probably or definitely related to Lenalidomide, the following criteria for retreatment and dose modification should be followed. The treating investigator should determine the clinical significance of laboratory values or radiographic findings and attribution to study medications before a treatment decision is made. Treatment may be held for a maximum of 21 days. Refer to Table 4 for dose reduction levels for Lenalidomide.

Dose delays and modifications will be made as indicated in the following table(s). The descriptions and grading scales found in the revised NCI Common Terminology Criteria for Adverse Events (CTCAE) version 4.0 will be utilized for dose delays and dose modifications. A copy of the CTCAE version 4.0 can be downloaded from the CTEP website [http://ctep.cancer.gov/protocolDevelopment/electronic\\_applications/ctc.htm](http://ctep.cancer.gov/protocolDevelopment/electronic_applications/ctc.htm).

## Hematologic Toxicities

CTCAE 4.0 Category	CTCAE Grade	Lenalidomide Dose Modification
Absolute Neutrophil Count (ANC)	Grade 1 or Grade 2	Continue to treat- Do NOT OMIT and DO NOT REDUCE therapy
	Grade 3	Hold dose Administer Filgrastim Resume at same dose when ANC is $\geq$ 1000 if neutropenia is the only hematologic toxicity If other hematologic toxicity $\geq$ Grade 2 is present, reduce dose one level when ANC $\geq$ 1000
	Grade 4	Hold dose Administer Filgrastim Resume therapy at one dose level lower when ANC is $\geq$ 1000
Neutropenia with Fever  ANC <1000 and temperature $\geq$ 38.5° C or 101°F	Grade 3 or Grade 4	Hold dose Administer Filgrastim Reduce dose one level when ANC $\geq$ 1000
Thrombocytopenia  Aspirin prophylaxis should be held if platelets are $\leq$ 50,000	Grade 1 or Grade 2	Continue to treat- Do NOT OMIT and DO NOT REDUCE therapy
	Grade 3 or Grade 4	Provide platelet transfusion support Redraw platelets  If redrawn platelet value $\geq$ 50,000 -> Do NOT OMIT and DO NOT REDUCE therapy  If redrawn platelet value $<$ 50,000 continue to transfuse at the discretion of the investigator and hold therapy until platelets are $\geq$ 50,000 on Day 1 or $\geq$ 30,000 intracycle

CONFIDENTIAL

This document is confidential. Do not disclose or use except as authorized.

		Resume therapy at one dose level lower when the patient's platelets are $\geq 50,000$ on Day 1 or $\geq 30,000$ intracycle
Anemia	Grade 1	Continue to treat- Do NOT OMIT and DO NOT REDUCE therapy
	Grade 2	Transfuse at the discretion of treating investigator
	Grade 3	
	Grade 4	Hold treatment Transfuse Resume treatment when hemoglobin $\geq 8.0$ g/dL DO NOT REDUCE therapy

 ANC can be calculated two ways: From the percentage of neutrophils: White Blood Count (WBC) x total neutrophils (polys% + bands%) x 10. From the absolute number of cells: (Absolute polys + Absolute bands) x 10.

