## Non Hematologic Toxicities

CTCAE 4.0 Category	CTCAE Grade	Lenalidomide Dose Modification
Infection or Viral Illness with ANC <math>\geq 1000</math>  Including herpes zoster reactivation	N/A	Day 1 of Cycle: Delay cycle until infection/viral illness has resolved. Resume treatment at the same dose level. Do not dose reduce.  Intracycle: Hold lenalidomide for a maximum of 21 days to allow for recovery. Resume treatment at same dose level.  If patient has delay of greater than 21 days, the patient must come off-study
Infection or Viral Illness with ANC <math>< 1000</math>	N/A	Day 1 of Cycle: Delay cycle until infection/viral illness has resolved. Administer filgrastim or equivalent as indicated.  Reduce one dose level when infection/virus has resolved, and ANC $\geq 1000$  Intracycle: Hold lenalidomide for a maximum of 21 days. Reduce one dose level when infection/virus has resolved and ANC $\geq 500$  If patient has a delay of less than or equal to 21 days, dose reduce to next dose level. If patient has delay of greater than 21 days, the patient must come off-study
Allergic reaction or hypersensitivity to	Grade 1	Continue to treat- Do NOT OMIT and DO NOT REDUCE therapy

CONFIDENTIAL

This document is confidential. Do not disclose or use except as authorized.

Lenalidomide  Including Rash related to Lenalidomide	Grade 2	Continue to treat- Do NOT OMIT and DO NOT REDUCE therapy
	Grade 3 or Grade 4	Hold lenalidomide Follow at least weekly.  If toxicity resolves to $\leq$ grade 2, restart at next lower dose level

Renal/Metabolic  For all grades, provide hydration and other supportive care as needed at the discretion of the treating investigator	Grade 1	Continue to treat- Do NOT OMIT and DO NOT REDUCE therapy
	Grade 2	Hold Lenalidomide until $<$ grade 2 and resume treatment at the same dose level  If toxicity recurs, dose reduce one dose level at the treating investigator's discretion
	Grade 3 or Grade 4	Hold Lenalidomide until $<$ grade 2 and resume treatment with one dose level reduction  If the toxicity remains $\geq$ grade 3, omit dose and restart at subsequent scheduled visit with one dose level reduction  If treatment-related toxicity occurs on day one of the cycle, the cycle will be delayed.
Diarrhea, Constipation, Nausea, or Vomiting	Grade 1	Continue to treat- Do NOT OMIT and DO NOT REDUCE therapy

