## 10. STUDY CALENDAR

Screening evaluations are to be conducted within 28 days prior to initiation of registration. Protocol therapy should start as soon after registration as feasible. Baseline assessments are to be conducted on C1D1 of initial therapy and should be considered separate from screening evaluations. Evaluations need not be repeated for C1D1 if screening evaluations are performed within 7 days of registration. Scans and bone marrow assessments do not need to be repeated if performed within 6 weeks of registration. All assessments must be performed prior to administration of any study medication.. See below for detailed scheduled of assessments. Study medications will be administered according to the schedule and guidelines outlined in Section 5.

	Pre-registration		Cycles 1-24 (28 days) 				Follow Up 
Tests and procedures	≤ 28 days prior to registration	≤ 21 days prior to registration	Day 1 of all cycles	Days 8, 15 and 22 of cycles 1 & 2	Cycle 9 Day 1/ Or to confirm CR^9	End of Tx	Every 3 or 6 Months (+/- 28 days)
				Days 1 &15 from cycle 3-8			
History and exam, height, weight. Performance Status	X		X			X	(X)
Toxicity Notation			X			X	
Hematology group (WBC w/ diff, PLT, Hgb, ANC)		X	X	X		X	X
Chemistry 		X	X	X		X	X
Direct & total bilirubin 		X	X			X	
Free light chain assay		X	X			X	X
Serum and Urine Immunofixation (SPEP and UPEP) with quantitative immunoglobulins 		X	X			X	X
β2M, CRP, LDH		X				X	
Metastatic Bone Survey/ Spine MRI or PET/CT 	X					X	(X)
EKG		X				X	
Serum pregnancy test		X					
Unilateral bone marrow aspirate and biopsy 	X				X	X	(X)
Research bone marrow aspirate 	X 				X 	X 	(X)
Research Blood 	X 		X		X	X	(X)

1- Cycle 1, Day 1 laboratory values need to meet eligibility criteria

2- Direct bilirubin to be obtained if total bilirubin is abnormal.

3- Scheduling allows for +/- 3 days cycles 1-2 and +/- 7 days for cycle 3 and beyond.

4- Chemistry includes sodium, potassium, chloride, bicarbonate, bun, creatinine, calcium, glucose, albumin, ALT (SGPT), total protein, AST (SGOT), total bilirubin, magnesium, and phosphorus.

5- These procedures should also be done at any time during the course of the study to confirm CR.

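### The second ANC formula in the lenalidomide dose-modification footnotes uses a multiplier of 10 that is wrong in either usual laboratory unit

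*Combined protocol and SAP*

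**What the plan says.** Section 6.2 gives two lenalidomide dose-modification tables, Hematologic Toxicities and Non Hematologic Toxicities. Each carries the same footnote 1, which offers a choice of two methods for the ANC.

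- The first method starts from the differential in percent: "From the percentage of neutrophils: White Blood Count (WBC) x total neutrophils (polys% + bands%) x 10".
- The second method, the one at issue here, starts from absolute counts: "From the absolute number of cells: (Absolute polys + Absolute bands) x 10".

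Neither formula states a unit. The eligibility criterion in section 3.1.5 sets ANC at 1000/µL or more, so the output is meant to be in cells/µL.

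The footnote marker sits on the ANC row of the hematologic table and on both infection rows of the non-hematologic table. Those rows act on printed ANC values:

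- **Grade 4 neutropenia:** "Resume therapy at one dose level lower when ANC is" at least 1000. Grade 3 restarts at the same threshold.
- **Infection, ANC 1000 or above, Day 1:** "Resume treatment at the same dose level. Do not dose reduce".
- **Infection, ANC below 1000, Day 1:** "Reduce one dose level when infection/virus has resolved, and ANC" is at least 1000. The intracycle restart for this row is at 500.

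The febrile-neutropenia row is defined by "ANC <1000 and temperature" of at least 38.5 °C. It uses the same ANC figure but has no footnote marker.

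**The concern.** Both formulas use a factor of 10, but they start from different quantities. In the first, 10 combines a conversion from thousands of cells (x 1000) with a conversion from percent (÷ 100). In the second the counts are already absolute, so there is no percent to remove and no evident reason for a 10. If so, the protocol prints two methods that disagree on the same blood sample.

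What is at stake is lenalidomide dosing in neutropenic patients. If a site entered cells/µL, the inflated ANC could have these effects:

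- **Ordinary neutropenia rows.** A site that used the formula throughout would understate the neutropenia and might never start the hold. A site that detected neutropenia from a correct ANC and then used the formula to judge recovery could restart early.
- **Febrile-neutropenia row.** The below-1000 definition could be missed, and with it the hold, filgrastim and one-level reduction. This is an inference, because the row does not carry the footnote marker.
- **Infection rows.** A patient could be placed in the same-dose row instead of the reduce-one-level row. This effect is narrow. Both rows delay the cycle on Day 1 and hold lenalidomide within the cycle. They differ in the one-level reduction, the ANC restart condition and the use of filgrastim.

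Isolated grade 3 neutropenia restarts at the same dose in any case, so no reduction is lost there. If a site entered 10^3/µL, the error would run toward withholding drug.

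**Working it through.** **Inputs.** The two formulas come from footnote 1. The output unit, cells/µL, comes from section 3.1.5. The thresholds 1000 and 500 are as printed in the section 6.2 tables. Assumption: absolute counts are reported in cells/µL or in 10^3/µL (the same as 10^9/L), since the footnote names no unit. No CTCAE grade cut-off is used.

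**Definition.** True ANC (cells/µL) = WBC (cells/µL) x (polys% + bands%) ÷ 100.

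**Formula 1, WBC in 10^3/µL.** True ANC = WBC x 1000 x % ÷ 100 = WBC x % x 10. The printed factor of 10 is reproduced. Example: 2.0 x (40 + 5) x 10 = 900/µL.

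**Formula 2, required factor.**

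- Counts in cells/µL: ANC = sum x 1.
- Counts in 10^3/µL: ANC = sum x 1000.

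The printed factor of 10 is reproduced in neither unit. It would be right only for counts reported in tens of cells/µL, which is not a usual unit.

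**Size of the error.** Printed ÷ required: 10 ÷ 1 = 10 (cells/µL), and 10 ÷ 1000 = 0.01 (10^3/µL).

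| True ANC (/µL) | Formula 2, cells/µL input | Formula 2, 10^3/µL input |
|---|---|---|
| 50 | 500 | 0.5 |
| 100 | 1,000 | 1 |
| 400 | 4,000 | 4 |
| 700 | 7,000 | 7 |
| 900 | 9,000 | 9 |
| 999 | 9,990 | 9.99 |
| 2,000 | 20,000 | 20 |

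**Same sample, both formulas.** WBC 1.0 x 10^3/µL, 70% neutrophils. Formula 1: 1.0 x 70 x 10 = 700. Formula 2: 700 x 10 = 7,000, or 0.70 x 10 = 7.

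**Against the printed thresholds.**

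- Cells/µL input: a true ANC of 100 to 999 reads 1,000 to 9,990 and passes the 1000 threshold. A true ANC of 50 to 499 reads 500 to 4,990 and passes the intracycle infection threshold of 500.
- 10^3/µL input: a reading of 1000 needs a true ANC of 1000 x 100 = 100,000/µL, so in practice the restart condition could not be met.

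**Would it be noticed?** With cells/µL input, the result exceeds total WBC when 10 x ANC > WBC, that is, whenever neutrophils are more than 10% of WBC.

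**The case against.** The arithmetic is not disputed. The case on the other side concerns a possible printing artefact, detectability and consequence.

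- **Lost superscript.** If the source read 10^3, formula 2 would be right for counts in 10^3/µL. This is possible but unsupported: superscripts survive elsewhere in the text, including the marker on this footnote, and both copies print a plain 10. The PDF page would settle it. Even then, the input unit would need to be stated.
- **Redundancy.** The study calendar in section 10 lists ANC itself under "Hematology group (WBC w/ diff, PLT, Hgb, ANC", so a site need not calculate it. The footnote is permissive and its first method is correct. This stands and is the main reason the practical risk is low.
- **Detectability.** A normal ANC of 2,000 would read 20,000 or 20. The latter fails the eligibility threshold, which the calendar also applies to Cycle 1 Day 1 values. A site using formula 2 would often meet an implausible number before any dose decision. This stands too, although nothing in the plan requires such a check.
- **Scope and judgement.** The rules in section 6.2 apply to events at least possibly related to lenalidomide. For non-hematologic events, "The treating investigator should determine the clinical significance of laboratory values or radiographic findings". That is a safeguard, but it does not correct the formula.
- **Early restart presupposes a hold.** With consistent use of formula 2 in cells/µL, a missed hold is the more direct effect. Early restart needs either a true ANC that first fell below 100 or a switch of method. That is correct, and the effects on the neutropenia rows should be read with those conditions.

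**Conclusion.** The second formula is wrong as written, in both footnotes. It reads 10 times too high for counts in cells/µL and 100 times too low for counts in 10^3/µL, and it contradicts the correct first formula on the same sample. The only assumption is that laboratories report in one of those two units.

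Severity is minor. The error lies in an operative dosing instruction, so it deserves correction, but the practical risk is low. No number of affected patients can be derived, and nothing in the documents shows that any site used the formula. The primary endpoint (section 13.1) and the safety stopping rule (section 13.5), which counts certain grade 3 organ-function events and grade 4/5 non-hematologic events, do not use ANC. There is no effect on sample size or on the primary analysis.

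**What to change.** Replace footnote 1 under both lenalidomide tables with wording to this effect: use the laboratory-reported ANC where available; otherwise ANC (cells/µL) = WBC (10^3/µL) x (polys% + bands%) x 10; or absolute polys + absolute bands if reported in cells/µL; or that sum x 1000 if reported in 10^3/µL. Send sites a short note of the correction.

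The cost is one line in each of two footnotes plus the site note. No procedure, assessment or analysis is added.

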## Non Hematologic Toxicities

CTCAE 4.0 Category	CTCAE Grade	Lenalidomide Dose Modification
Infection or Viral Illness with ANC <math>\geq 1000</math>  Including herpes zoster reactivation	N/A	Day 1 of Cycle: Delay cycle until infection/viral illness has resolved. Resume treatment at the same dose level. Do not dose reduce.  Intracycle: Hold lenalidomide for a maximum of 21 days to allow for recovery. Resume treatment at same dose level.  If patient has delay of greater than 21 days, the patient must come off-study
Infection or Viral Illness with ANC <math>< 1000</math>	N/A	Day 1 of Cycle: Delay cycle until infection/viral illness has resolved. Administer filgrastim or equivalent as indicated.  Reduce one dose level when infection/virus has resolved, and ANC $\geq 1000$  Intracycle: Hold lenalidomide for a maximum of 21 days. Reduce one dose level when infection/virus has resolved and ANC $\geq 500$  If patient has a delay of less than or equal to 21 days, dose reduce to next dose level. If patient has delay of greater than 21 days, the patient must come off-study
Allergic reaction or hypersensitivity to	Grade 1	Continue to treat- Do NOT OMIT and DO NOT REDUCE therapy

CONFIDENTIAL

This document is confidential. Do not disclose or use except as authorized.

Lenalidomide  Including Rash related to Lenalidomide	Grade 2	Continue to treat- Do NOT OMIT and DO NOT REDUCE therapy
	Grade 3 or Grade 4	Hold lenalidomide Follow at least weekly.  If toxicity resolves to $\leq$ grade 2, restart at next lower dose level

Renal/Metabolic  For all grades, provide hydration and other supportive care as needed at the discretion of the treating investigator	Grade 1	Continue to treat- Do NOT OMIT and DO NOT REDUCE therapy
	Grade 2	Hold Lenalidomide until $<$ grade 2 and resume treatment at the same dose level  If toxicity recurs, dose reduce one dose level at the treating investigator's discretion
	Grade 3 or Grade 4	Hold Lenalidomide until $<$ grade 2 and resume treatment with one dose level reduction  If the toxicity remains $\geq$ grade 3, omit dose and restart at subsequent scheduled visit with one dose level reduction  If treatment-related toxicity occurs on day one of the cycle, the cycle will be delayed.
Diarrhea, Constipation, Nausea, or Vomiting	Grade 1	Continue to treat- Do NOT OMIT and DO NOT REDUCE therapy
	Grade 2	Treat at the discretion of the investigator  Provide aggressive supportive care  DO NOT REDUCE therapy
	Grade 3	Hold Lenalidomide until toxicity resolves to $<$ grade 2  If the patient has received maximum supportive care, resume therapy with one dose level reduction
	Grade 4	Hold Lenalidomide until toxicity resolves to $<$ grade 2  Resume therapy with one dose level reduction

CONFIDENTIAL

This document is confidential. Do not disclose or use except as authorized.

--	--	--

All other related toxicities not listed previously in this table	Grade 1	Continue to treat- Do NOT OMIT and DO NOT REDUCE therapy
	Grade 2	Continue to treat- Do NOT OMIT and DO NOT REDUCE therapy unless considered to be a clinically significant finding  Provide supportive care as needed
	Grade 3	Hold Lenalidomide until toxicity resolves to < grade 2  Resume therapy with one dose level reduction at the discretion of the treating investigator
	Grade 4	Hold Lenalidomide until toxicity resolves to < grade 2  Resume therapy with one dose level reduction  If treatment-related toxicity occurs on day one of the cycle, the cycle will be delayed.  If patient has a delay of less than or equal to 21 days, dose reduce to next dose level. If patient has delay of greater than 21 days, the patient must come off-study

 ANC can be calculated two ways: From the percentage of neutrophils: White Blood Count (WBC) x total neutrophils (polys% + bands%) x 10. From the absolute number of cells: (Absolute polys + Absolute bands) x 10

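### Section 6.2 sets two ANC thresholds (500 and 1000) for restarting lenalidomide after a mid-cycle infection with ANC below 1000, and does not say which governs; the restart dose also conflicts in one narrow case.

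*Combined protocol and SAP*

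**What the plan says.** Section 6.2 (Lenalidomide) gives one table for hematologic and one for non-hematologic toxicities. Each is introduced by the same instruction, that "the following criteria for retreatment and dose modification should be followed", and each applies only to events judged at least possibly related to lenalidomide.

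The Non Hematologic Toxicities table has a row for infection or viral illness with ANC below 1000:
- On Day 1 of a cycle: "Reduce one dose level when infection/virus has resolved, and ANC $\geq 1000".
- Intracycle: "Reduce one dose level when infection/virus has resolved and ANC $\geq 500".
- For longer delays: "If patient has delay of greater than 21 days, the patient must come off-study".

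The Hematologic Toxicities table addresses the same neutrophil counts, with no Day 1/intracycle split:
- ANC Grade 3, nothing else: "Resume at same dose when ANC is $\geq$ 1000 if neutropenia is the only hematologic toxicity".
- ANC Grade 3 with another hematologic toxicity of Grade 2 or more: "reduce dose one level when ANC $\geq$ 1000".
- ANC Grade 4: "Resume therapy at one dose level lower when ANC is $\geq$ 1000".
- Neutropenia with Fever (ANC below 1000 plus a temperature criterion): one level lower, again once ANC is at least 1000.

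These neutropenia rows also direct filgrastim. The infection row mentions filgrastim only in its Day 1 part.

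**The concern.** A patient with a mid-cycle infection and ANC below 1000 meets the infection row and at least one neutropenia row. Both tables are to be followed, and nothing in Section 6.2 ranks them. Sections 6.1 and 6.4.3, which deal with held elotuzumab, do not settle it either.

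Two sites could therefore treat the same patient differently while each follows the protocol. At ANC 500 to 999 one could restart and the other keep holding. In one subgroup they could also restart at different doses. On the ANC criterion alone, a patient just recovered from infection has a looser rule than an uninfected patient with the same count.

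The situation is foreseeable. Section 7.1.1.2 lists neutropenia and upper respiratory infection each in more than 10% of lenalidomide-treated patients, and the Study Calendar schedules mid-cycle blood counts in cycles 1 to 8.

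**Working it through.** The plan states no figure to reproduce. The check sets the rows side by side for infection plus ANC below 1000, both events at least possibly related to lenalidomide.

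**Mid-cycle**

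| Neutropenia row also met | ANC to restart: infection row | ANC to restart: neutropenia row | Dose: infection row | Dose: neutropenia row |
|---|---|---|---|---|
| Grade 3, afebrile, only hematologic toxicity | 500 | 1000 | one level lower | same dose |
| Grade 3 with another hematologic toxicity of Grade 2 or more | 500 | 1000 | one level lower | one level lower |
| Grade 4 | 500 | 1000 | one level lower | one level lower |
| Neutropenia with Fever | 500 | 1000 | one level lower | one level lower |

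**Timing.** The infection row releases the drug when infection has resolved and ANC is at least 500. The neutropenia rows hold it while ANC is below 1000. Both conditions are true when 500 ≤ ANC < 1000, so the thresholds disagree in every mid-cycle line. On Day 1 both tables require 1000 and there is no timing conflict.

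**Dose.** The tables disagree only in the first line. That disagreement also arises on Day 1, because the infection row's Day 1 rule reduces one level too.

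**Size of the dose difference.** Table 4 starts at 25 mg, and its first reduction is 20 mg. For a patient on 25 mg in cycles 1 to 8:
- Daily difference: 25 − 20 = 5 mg, and 5/25 = 20%.
- For a mid-cycle restart on day d of the 21 dosing days, assuming held days are not made up, 22 − d doses remain. The difference in that cycle is 5 × (22 − d) mg.
- At d = 15, 7 doses remain: 7 × 25 = 175 mg against 7 × 20 = 140 mg, a difference of 35 mg.
- Over d = 2 to 21 the difference runs from 5 × 20 = 100 mg down to 5 × 1 = 5 mg.

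**Effect of the grade boundaries.** The documents cite CTCAE 4.0 without printing its cut-offs. If Grade 3 is taken as ANC 500 to 999, a patient who stays in Grade 3 already meets the infection row's count. That row then permits restart on resolution of the infection alone.

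**The case against.** The strongest reply is that the infection row names the exact combination, infection with ANC below 1000, and carries its own hold, threshold, dose step and time limit. If the neutropenia rows overrode it, the intracycle value of 500 would rarely have any effect. The value may well be deliberate: the thrombocytopenia row of the other table also relaxes its threshold mid-cycle ("hold therapy until platelets are $\geq$ 50,000 on Day 1 or $\geq$ 30,000 intracycle"). A site could reasonably let the infection row govern.

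That reading is sensible, but the text does not settle it. Neutropenia with Fever is also a combined category and it requires 1000. A febrile, infected, neutropenic patient meets both rows, with different thresholds. The platelet row states its two values in its own table and no other row contradicts them, whereas 500 is contradicted by three rows.

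Three further points on the other side stand:
- A site that waits for ANC of at least 1000 within 21 days satisfies both tables on timing.
- The looser count is paired with a mandatory dose reduction, whereas uninfected isolated Grade 3 neutropenia resumes at full dose. A reader might infer that infected patients get the less cautious rule overall; the text does not support that.
- The non-hematologic preamble leaves attribution and the clinical significance of laboratory and radiographic findings to the treating investigator, which narrows the overlap.

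**Conclusion.** The inconsistency is real and minor. The restart threshold conflicts for every mid-cycle infection with ANC below 1000 when both events are attributed to lenalidomide. The restart dose conflicts only for afebrile Grade 3 neutropenia that is the sole hematologic toxicity, mid-cycle or on Day 1. From 25 mg that is a 20% difference in daily dose.

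Two stronger conclusions might be drawn, and neither is supported. One is that the tables disagree on dose in general; in the other cases both say one level lower. The other is that 500 is a mistake; it may be intended, and the defect is that it is not stated as an exception.

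The number of patients affected cannot be derived from the documents, which give no joint rate of infection and neutropenia. Sample size and the primary analysis are unaffected. The dose totals assume a 25 mg starting dose and held days not made up.

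**What to change.** Add one sentence to both Section 6.2 tables, for example:

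*When infection or viral illness and ANC < 1000 occur together, the Infection with ANC < 1000 row sets the restart dose (one level lower), and the filgrastim direction of the neutropenia rows still applies; restart when infection has resolved and ANC ≥ 1000.*

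Change the intracycle 500 in the infection row to match. If the sponsor intended 500 mid-cycle, keep it and state it in that sentence as an explicit exception to the ANC Grade 3, ANC Grade 4 and Neutropenia with Fever rows. The filgrastim clause is needed because the infection row's intracycle part is silent on it, so letting that row simply replace the others would drop the direction for these patients.

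The cost is a short protocol amendment. Confirming 500 adds no hold time. Choosing 1000 lengthens some mid-cycle holds, and a few could reach the row's 21-day off-study limit; Section 5.4.1 caps filgrastim at 3 doses per week. The opening of Section 6.2 allows longer holds with the overall principal investigator's approval, but this row says the patient must leave the study. The amendment should state whether that approval applies to this row.

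### The Renal/Metabolic Grade 3-4 lenalidomide cell adds a restart by visit date with no recovery condition, and does not say that its own below-grade-2 rule still governs

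*Combined protocol and SAP*

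**What the plan says.** The Renal/Metabolic row of the Non Hematologic Toxicities table in section 6.2 has one cell for Grades 3 and 4, with three instructions.

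- First sentence: "Hold Lenalidomide until $<$ grade 2 and resume treatment with one dose level reduction".
- Second sentence: "If the toxicity remains $\geq$ grade 3, omit dose and restart at subsequent scheduled visit with one dose level reduction".
- Third sentence: "If treatment-related toxicity occurs on day one of the cycle, the cycle will be delayed".

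The Grade 2 line of the same row reads: "Hold Lenalidomide until $<$ grade 2 and resume treatment at the same dose level".

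The text at the start of section 6.2 limits a hold to 21 days, or longer if the overall principal investigator approves. It also asks the treating investigator to judge clinical significance and attribution before deciding on treatment. Section 5.2 refers to section 6.2 for the lenalidomide pre-treatment criteria, so this table is the working rule at the sites.

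**The concern.** The first sentence makes restart depend on recovery. The second makes it depend on the calendar, and it is addressed to the patient who has not recovered. A site that follows the second sentence as written can resume lenalidomide at the next visit without asking whether the toxicity has fallen below grade 2.

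Two things are at stake. One is safety: section 7.1.1.2 lists renal failure among lenalidomide events, and resuming the drug during unresolved renal or metabolic toxicity is what the first sentence is there to prevent. The other is consistency: in a multi-center trial, two sites could treat the same patient differently and each point to the cell in support.

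**Working it through.** No arithmetic applies and the plan states no figure on this point. The check is to apply each reading to the same patient, then look for anything elsewhere that settles the matter.

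**Step 1. Apply the readings.** Take a patient with grade 3 or 4 renal toxicity that persisted, so that the dose was omitted. Consider the grade at the next scheduled visit.

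| Grade at that visit | First sentence alone | Second sentence, literal | Second sentence, omission re-applied at each visit | First sentence governs throughout |
|---|---|---|---|---|
| 3 or 4 | Hold | Restart one level lower | Omit again | Hold |
| 2 | Hold | Restart one level lower | Unclear: restart by visit date, or hold under the Grade 2 line | Hold |
| Below 2 | Restart one level lower | Restart one level lower | Restart one level lower | Restart one level lower |

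The readings agree once the toxicity is below grade 2. They part at grade 2 and, on the literal reading, at grade 3 or 4 as well. The cell does not say which reading is meant.

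**Step 2. Look for a tie-breaker.**

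- The 21-day limit in section 6.2, with or without extension, governs how long a hold may last. It gives no grade for restart.
- The investigator's judgement in section 6.2 concerns significance and attribution. It sets no recovery threshold.
- The third sentence of the cell delays a cycle for toxicity on Day 1. It does not say at what grade the cycle may then begin.
- Section 5.5 allows removal from therapy for unacceptable adverse events or at the investigator's judgement. Sections 7.3 and 7.4 require expedited reporting. Neither sets a restart grade.
- The calendar in section 10 requires laboratory values to meet the eligibility criteria at Cycle 1 Day 1 only, so eligibility limits are no backstop later.

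None of these ranks the two sentences.

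**Step 3. Compare neighbouring cells.**

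- Allergic reaction, Grade 3 or 4: "If toxicity resolves to $\leq$ grade 2, restart at next lower dose level".
- All other related toxicities, Grade 3 and Grade 4: "Hold Lenalidomide until toxicity resolves to $<$ grade 2".
- Neutrophils, Grade 4: "Resume therapy at one dose level lower when ANC is $\geq$ 1000".
- Platelets, Grade 3 or 4: "hold therapy until platelets are $\geq$ 50,000 on Day 1 or $\geq$ 30,000 intracycle".

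Each ties restart to recovery. Where a lower bar is accepted within a cycle, as for platelets, it is given as a number. The comparison has limits. The gastrointestinal Grade 3 cell also has a second sentence without a grade, and the cell for infection with adequate neutrophils resumes mid-cycle without restating recovery. Neither, however, sets a restart visit for a patient whose toxicity persists.

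**Step 4. See when it could arise.** Scheduled visits fall on Days 1, 8, 15 and 22 in cycles 1-2, and lenalidomide is given on Days 1-21 (sections 5.1 and 10). A toxicity found on Day 8 therefore has its next visit on Day 15, 15 - 8 = 7 days later and still a dosing day. Where the next visit is a Day 1, the third sentence may delay the cycle instead. The exposed window is mainly mid-cycle.

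**The case against.** The strongest reply is that the cell can be read as a coherent whole. The first sentence sets the threshold. The second adds only that doses missed while toxicity persists are not made up, and that restart waits for a scheduled visit at a reduced dose. The third covers Day 1. Repeating the omission at each visit would keep a patient at grade 3 or higher off drug, and the Grade 2 line of the row would hold a patient who had improved to grade 2. Investigator judgement, removal for unacceptable events and expedited reporting also make careless re-dosing less likely. It might be added that a looser rule could be intended, since the allergic-reaction row restarts at grade 2.

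Much of this stands. The reconciling reading is reasonable, and the sentences are not in proven contradiction. A reader might infer that the protocol authorises dosing during grade 3 or 4 renal toxicity. The documents do not support that: only the fully literal reading gives it, and the instruction to omit the dose points the other way. What remains is that the cell never states the reconciling reading, that the safeguards supply no restart grade, and that a looser threshold, if wanted, is nowhere stated.

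**Conclusion.** The point holds as a narrow wording defect with a safety consequence. Followed literally, the second sentence permits restart by visit date while renal or metabolic toxicity is still grade 2 or higher. The conclusion rests on the wording of the cell and on the absence of any rule elsewhere that ranks its sentences or sets a restart grade.

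Its size should not be put into numbers. A reader might try to count exposed visits or extra lenalidomide doses from the calendar and the dose-reduction table. Any such count depends on when toxicity is judged to remain, and on whether the Day 1 delay covers toxicity that began earlier. The documents settle neither, and they give no rate of grade 3-4 renal or metabolic events for this regimen in this population. The primary endpoint, sample size and error rates are untouched.

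**What to change.** Replace the second sentence of the Renal/Metabolic Grade 3 or 4 cell with:

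*If the toxicity remains >= grade 3, omit the dose, reassess at each subsequent scheduled visit, and restart with one dose level reduction only once the toxicity is < grade 2.*

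This uses the row's own threshold and keeps the one-level reduction. Leave the 21-day hold rule in section 6.2 to apply unchanged; the defect can be cured without touching it.

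The cost is one sentence in one table cell at the next amendment. No visits or tests are added, because chemistry is already scheduled at these visits. The downside is that some patients may miss a few more lenalidomide doses than under the literal reading of the present text.
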